6.1.2 Consumption of Study Product (Oral AC)

Participants will report to the University of Minnesota Health Clinical Research Unit (CRU) on a daily basis and consume the assigned combination of oral AC. Each participant will drink an assigned combination every day for 3 consecutive days (M/T/W) and switch to a different assigned combination for the 3 days (M/T/W) the following week. Subjects will drink AC in sitting position. Subjects must stay in the research unit for 15 minutes after consuming AC to be observed for aspiration.

6.1.3 Experience Rating

After drinking the solution, each subject will rate their experience using a 5-point scale (1=terrible, 2=bad, 3=okay, 4=good, 5=great) every day (Appendix III). They will be asked to do this daily starting day 1 (Mon of week 1) through day 12 (Friday of week 2).

6.1.4 Compensation

Each of the healthy volunteers participating this pilot study will receive an Amazon gift card for \$50.

6.2 Subject Monitoring

Healthy volunteers will be observed for fifteen minutes after consuming the AC. Upon leaving the research unit, they will have access to the CRA via phone. For 2 days after each round of study product consumption, a member of the study team will contact the subject and screen for all grade 2 or higher AEs and SAEs.

Subjects with an adverse event will be followed until the event has resolved or stabilized with sequelae.

6.3 Management of Selected Expected Toxicities

Toxicity data is based on studies using pharmaceutical grade AC for treatment of intentional overdose/poison control. These doses are much higher than the planned doses of medical grade AC on this protocol. Lower doses are thought to be more tolerable.

- The most common toxicity of AC (doses used for poisoning treatment) is nausea/vomiting, ranging from 15-27%.
- Pulmonary aspiration is the most serious complication, occurring in <1% of patients. AC will not be administered to patients at risk for aspiration.

It should be noted that the cause of aspiration is multifactorial, and part of the risk reported in studies should be contributed to the effect of toxin or the loss of protective reflexes in cases of poisoning. We do not expect these to be present in our participants.

6.4 Supportive Care

No specific supportive care is needed.

6.5 Duration of Study Participation

Participants will be involved for 12 days over a 2 week period including 6 days of active study participation and 4 days of study team follow-up.

6.6 Withdrawal from Study

Participants have the right to withdraw consent at any time by informing a member of the study staff or by following the instructions provided in the HIPAA document.

7 Schedule of Activities

	Screening Visit	Week 1-2
Consent and eligibility screening	Х	
Physical Exam	Х	
Drink Study product in either tap water, protein shake, or apple juice (per table 1*)		M, T, W
Rate Experience (taste test)		M, T, W
Screen for AEs		M, T, W
Telephone call from study staff to check for AEs		Th, F

8 Study Product Information

8.1 Medical Grade Activated Charcoal

8.1.1 Other Names

Medical grade AC, "Activated Charcoal Powder, USP", activated carbon.

8.1.2 Description

Activated Charcoal, Powder, USP is carbon that has been treated to create low-volume pores that increase the area available for chemical reactions and adsorption. The most common pharmaceutical uses of activated charcoal is as a purification agent and antitoxin. All Spectrum Chemical USP products are manufactured, packaged and stored under current Good Manufacturing Practices (cGMP) per 21CFR part 211 in FDA registered and inspected facilities.

8.1.3 Mode of Action

Hemoperfusion through columns of activated charcoal to remove endogenous or exogenous toxins in uremia, hepatic failure, or acute toxicity associated with overdose of certain drugs.

8.1.4 Availability

Medical grade AC, "Activated Charcoal Powder, USP" will be purchased from Spectrum Chemical MFG Corporation. https://www.spectrumchemical.com Spectrum is an FDA registered manufacturer and distributor of chemicals and laboratory products.

8.1.5 Storage

As per the Spectrum Safety Data Sheet, the container of AC should be kept tightly closed in a dry and well-ventilated place. The container should be stored at room temperature.

8.1.6 Preparation and Administration

A member of the study team will make a suspension using 12g or 25g, or 50g of AC mixed with 4 oz. of either tap water or apple juice. The solutions will be administered as per section

8.1.7 Toxicities

GI Effects

May cause vomiting, constipation, diarrhea, and GI obstruction or fecal impaction in dehydrated patients.

Generally should not be used when decreased peristalsis present (reduced or absent bowel sounds); if risk of GI obstruction, perforation, or hemorrhage exists; if surgery has occurred recently; or if electrolyte imbalance or volume depletion exists.

Pulmonary Effects

Aspiration of activated charcoal may lead to more severe complications than aspiration of gastric contents alone. Aspiration from vomiting or misdirected nasogastric catheter has resulted in granulomatous reactions, bronchiolitis obliterans, tissue reaction to suspension agents (sorbitol, povidone), increased lung permeability, and rarely, death.

Use of Fixed Combination

When used in fixed combination with other agents, consider the cautions, precautions, and contraindications associated with the concomitant agents.

Common Adverse Effects

Vomiting, diarrhea, constipation, black stools.

9 Event Monitoring, Documentation and Reporting

Toxicity and adverse events will be classified and graded according to NCI's Common Terminology Criteria for Adverse Events version 5.0 (CTCAE V5) and reported on the schedule

below. A copy of the CTCAE can be downloaded from the CTEP home page. (http://ctep.cancer.gov/protocolDevelopment/electronic applications/ctc.htm#ctc 50).

The following definitions of adverse events (AEs) and serious adverse events (SAEs) will determine whether the event requires expedited reporting via the SAE Report Form in addition to routine documentation in the OnCore AE case report form (CRF).

Note: throughout this section the generic term "study drug" refers to study product, medical grade Oral AC.

9.1 Event Terminology

Adverse Event: Any untoward medical occurrence associated with the use of a drug in humans, whether or not considered drug related.

Serious Adverse Event: An adverse event is considered "serious" if, in the view of either the investigator or sponsor, it results in any of the following outcomes:

- Death
- A life-threatening adverse experience
- Inpatient hospitalization or prolongation of existing hospitalization
- A persistent or significant incapacity or substantial disruption of the ability to conduct normal life functions
- A congenital anomaly/birth defect
- Important medical events that may not result in death, be life-threatening, or require hospitalization may be considered serious when, based upon appropriate medical judgment, they may jeopardize the patient or subject and may require medical or surgical intervention to prevent one of the outcomes listed in this definition.

Unexpected Event: An adverse event or suspected adverse reaction is considered "unexpected" if it is not listed in protocol-related documents (e.g. protocol, consent documents, investigator brochure, package insert), or is not listed at the specificity or severity that has been observed or given the characteristics of the subject population being studied.

Attribution: is the relationship between an adverse event or serious adverse event and the study drug. Attribution is assigned as follows:

- Definite The AE is clearly related to the study drug
- Probable The AE is likely related to the study drug
- Possible The AE may be related to the study drug
- Unlikely The AE is doubtfully related to the study drug

• Unrelated – The AE is clearly not related to the study drug Attribution must be assigned by the treating physician or the PI.

The following definitions are from the Masonic Cancer Center's Standard Operating Procedure (SOP) Deviation Reporting:

Major Deviation: A deviation or violation that impacts the risks and benefits of the research; may impact subject safety, affect the integrity of research data and/or affect a subject's willingness to participate in the research. Deviations that place a subject at risk, but do not result in harm are considered to be major deviations.

Minor Deviation: A deviation or violation that does not impact subject safety, compromise the integrity of research data and/or affect a subject's willingness to participate in the research.

9.2 Event Documentation

Participants will be monitored for adverse events from the 1st dose of study treatment through day 12. After that time point, events meeting the definition of serious and at least possibly related to study treatment will be documented upon knowledge.

We will collect the following Grade 2-5 adverse events attributable to AC:

Aspiration of activated charcoal

In addition any event meeting the definition of a serious adverse event (SAE) regardless of attribution that occurs during this period will be documented in the source document and recorded in OnCore.

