1.2 Secondary Objective

Determine the incidence of grade 2 and above SAEs deemed at least probably related to AC.

2 Background and Rationale

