2.4 Rationale

Investigators are looking for new ways to protect the microbiome during the period of antibiotic exposure, improve the safety of antibiotics and reduce the rate of dysbiosis-related complications in patients. Determining the palatability and tolerability of AC in healthy volunteers in this research will aid in the design of future trials to investigate the efficacy of AC in patients.

3 Study Design

We will use the powder form of medical grade oral AC and mix it with liquids for administration. 12 healthy volunteers will be enrolled to determine the two most palatable and tolerable AC combinations. There will be a total of 4 combinations (2 AC doses and 2 solutions) in stage 1. Each participant will drink an assigned combination every day for 3 consecutive days (Monday, Tuesday, Wednesday, "M/T/W") and switch to a different assigned combination M/T/W the following week. AC solution assignments will be defined before the study using a balanced incomplete block design. Each subject will rate their experience using a 5-point scale every day for the 12 days they are on study.

The following outcome variables will be measured:

- (i) Each healthy volunteer will rate their experience using a 5-point scale (1=terrible, 2=bad, 3=okay, 4=good, 5=great) every day.
- (ii) To evaluate tolerability, after each round of study product consumption, a member of the study team will contact the subject and screen for grade 2 or higher AEs and SAEs

4 Participant Selection

Study entry is open to adult volunteers regardless of gender or ethnic background. While there will be every effort to seek out and include women and minorities, the subject population is expected to reflect the population of Minnesota.

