11.2 Secondary Endpoint

Safety, defined by the incidence of grade 2 and above AEs deemed at least probably related to AC by day 12.

12 Statistical Considerations

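### Section 9.2 limits the non-serious grade 2-5 AEs collected to aspiration, which cannot supply the grade 2+ AE endpoint in 11.2; objective 1.2 counts SAEs where 11.2 counts AEs

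*Combined protocol and SAP*

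**What the plan says.** The relevant statements in the combined protocol and SAP are these.

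- **Collection (9.2, Event Documentation).** Monitoring runs from the first dose through day 12. The section then says "We will collect the following Grade 2-5 adverse events attributable to AC", and the list that follows has one entry, "Aspiration of activated charcoal". SAEs in the same period are also recorded, whatever their attribution.
- **Endpoint (11.2).** "Safety, defined by the incidence of grade 2 and above AEs deemed at least probably related to AC by day 12". The event type is not restricted.
- **Objective (1.2).** "Determine the incidence of grade 2 and above SAEs deemed at least probably related to AC".
- **Screening.** Section 3 gives as its tolerability outcome that "a member of the study team will contact the subject and screen for grade 2 or higher AEs and SAEs". Section 6.2 repeats this with a wider word: "a member of the study team will contact the subject and screen for all grade 2 or higher AEs and SAEs". The section 7 schedule has AE checks on the three dosing days and, on Thursday and Friday, a "Telephone call from study staff to check for AEs".
- **Expected effects.** Section 8.1.7 gives the common adverse effects as "Vomiting, diarrhea, constipation, black stools". Section 6.3 names nausea/vomiting as the most common toxicity, at 15-27% with poisoning doses, and puts aspiration below 1%.

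**The concern.** The section that governs what is recorded is narrower than the endpoint that has to be computed from the records. The schedule would detect a non-serious grade 2 vomiting episode judged probably related, and 11.2 would count it, but it is not on the 9.2 list. Nothing in the protocol says which section takes precedence.

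Staff who follow 9.2 would report an incidence built from aspiration and SAEs alone. Staff who follow 6.2 or 11.2 would report something larger. The safety result then depends partly on which section was followed, and the error under the literal reading runs one way: the product looks better tolerated than it was.

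The objective adds a separate ambiguity. Seriousness (9.1) is defined mainly by outcome, while grade is CTCAE severity. Grade 2+ SAEs and grade 2+ AEs are therefore different counts, and a report could meet one definition without answering the other.

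**Working it through.** **Plan's own figure.** The protocol gives no numerical figure for this point. The one design figure that can be checked is six subjects per combination, and it reproduces: 12 subjects × 2 combinations ÷ 4 = 6, which matches a count of the assignments in the 6.1.1 table.

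**Sections side by side.** Take a non-serious grade 2+ event judged at least probably related, by day 12:

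| Section | Aspiration | Vomiting, diarrhea, constipation |
|---|---|---|
| 3 and 6.2 (screening) | screened for | screened for |
| 9.2 (collection) | listed | not listed |
| 11.2 (endpoint) | counts | counts |
| 1.2 (objective) | does not count, not serious | does not count, not serious |

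The right-hand column is the defect: these events are screened for and belong to the endpoint, but they are outside the collection list and outside the objective as worded.

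**What the listed event can contribute.** Take aspiration at 1%, the upper limit of the range in 6.3:

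- Expected count: 12 × 0.01 = 0.12 subjects.
- Chance of at least one: 1 − 0.99^12 = 0.114.

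**What the unlisted events might contribute (illustration only).** The documents give no grade 2+ rate at 12 g or 25 g. Let r be the ungraded nausea/vomiting rate in 6.3 (0.15 to 0.27), and let s be an assumed share of those events that is grade 2+ and at least probably related. Treating subjects as independent,

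P(at least one of 12) = 1 − (1 − s·r)^12.

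| s (assumed) | r = 0.15 | r = 0.27 |
|---|---|---|
| 0.10 | 1 − 0.985^12 = 0.166 | 1 − 0.973^12 = 0.280 |
| 0.25 | 1 − 0.9625^12 = 0.368 | 1 − 0.9325^12 = 0.568 |
| 0.50 | 1 − 0.925^12 = 0.608 | 1 − 0.865^12 = 0.825 |

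These are chances that such an event occurs, not chances that it goes unrecorded. Section 6.3 says the source doses were much higher than those planned here, so the values may be too high.

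**Effect of one missed subject.** With 12 subjects, omitting one affected subject lowers the reported incidence by 1/12 = 8 percentage points, and omitting two lowers it by 2/12 = 17 points.

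**The case against.** The best defence is that the protocol, read as a whole, does intend to capture these events. Section 3 presents the screening as a measured outcome. The opening of section 9 applies CTCAE grading to adverse events generally and mentions routine entry on the OnCore AE form. Section 6.2 follows any subject with an adverse event until it resolves or stabilizes. Section 10.2 has the investigator and the biostatistician approve the CRF, and the Appendix II rating form asks about charcoal-related problems. Section 9.2 never uses the word only. On this view the text is loosely drafted and no data need be lost. This shows that the events would be noticed and probably graded. It does not settle the matter: none of these places says that non-serious events beyond the 9.2 list are recorded for the endpoint, and the rating form asks for neither grade nor attribution.

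A second point is that the 9.2 lead-in is plural but one item follows, so entries may have been lost in conversion from PDF. That is possible, though no gap is marked. Unless it was exhaustive, a longer closed list would still be narrower than the screening in 6.2, and the mismatch between 1.2 and 11.2 does not depend on it.

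Two further points stand. The conflict with sections 3 and 6.2 is softer than the one with 11.2, because screening and collecting are different acts. The illustrative probabilities rest on assumed shares and do not measure bias, so the seriousness of the point should not rest on them.

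**Conclusion.** The concern holds. As written, 9.2 does not collect the data that 11.2 needs, and 1.2 and 11.2 define different counts. If 9.2 is followed literally, the secondary safety incidence is biased toward zero. By how much is unknown. The illustration gives a chance of roughly 17% to 82% that at least one unlisted endpoint event occurs among 12 subjects, on assumed shares of 10% to 50% and a rate borrowed from higher doses.

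The consequence is limited. Only a descriptive secondary endpoint is affected, SAEs are recorded in any case, and 12.3 selects the combination on ratings, so the primary ranking does not change. It should still be corrected, because section 2.4 offers the tolerability findings as input to the design of later patient trials.

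**What to change.** - **9.2:** replace the one-item list with collection of all grade 2-5 AEs from first dose through day 12, each with attribution on the 9.1 scale. Keep aspiration as a named event of interest. Noting which combination the subject was taking is a useful addition, although 11.2 does not require it.
- **1.2:** change SAEs to AEs, so that the objective and the endpoint count the same thing.
- **AE CRF:** confirm that its scope matches the revised 9.2. The form is not in the documents; if it was built from 9.2 it will need widening.

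No visits, calls or subjects are added, because the screening in sections 3, 6.2 and 7 already asks for these events. The cost is two wording changes, a possible CRF revision and slightly more AE recording. The reported AE rate may also come out less favourable.

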9.3 SAE and Death Documentation

Any event meeting the definition of a serious adverse event (SAE) requires documentation using the MCC SAE Report Form in OnCore.

9.4 Expedited Event Reporting

Agency reporting to	Criteria for reporting	Timeframe	Form to Use	Submission address/email address
U of MN IRB	Unanticipated death of a locally enrolled subject(s); New or increased risk; Any adverse event that require a change to the protocol or consent form – refer to the IRB website for complete details	5 Business Days	IRB Report Form	[contact]

	Clinical deviations per current IRB reporting r	equirements	OnCore	
			Deviation Form	
Masonic Cancer Center SAE Coordinator	Events that meet the definition of dose limiting toxicity or an early study stopping rule	At time of reporting	Event Form	[contact]
	Unexpected and fatal or unexpected and life threatening suspected adverse reaction	no later than 7 Calendar Days		
FDA	1) Serious and unexpected suspected adverse reaction or 2) increased occurrence of serious suspected adverse reactions over that listed in the protocol or investigator brochure or 3) findings from other sources (other studies, animal or in vitro testing)	no later than 15 Calendar- Days	MCC SAE Report Form	Submit to FDA as an amendment to IND

10 Study Data Collection and Monitoring

10.1 Data Management

This study will collect regulatory and clinical data using University of Minnesota CTSI's instance of OnCore® (Online Enterprise Research Management Environment). The Oncore database resides on dedicated secure and PHI compliant servers. All relevant AHC IS procedures related for PHI compliant servers (as required by the Center of Excellence for HIPAA Data) apply to Oncore databases.

The data will be integrated and extracted to researchers through the CTSI Informatics team and will be delivered through secure and compliant mechanisms (e.g. AHC IE data shelter, BOX, sftp, etc). If data de-identification is needed, then compliant AHC IE data de-identification tools will be used. The informatics team will grant the IRB approved study team members access to data.

Key study personnel are trained on the use of OnCore and will comply with protocol specific instructions embedded within the OnCore.

10.2 Case Report Forms

Participant data will be collected using protocol specific electronic case report forms (e-CRF) developed within OnCore based on its library of standardized forms. The e-CRF will be approved by the study's Principal Investigator and the Biostatistician prior to release for use. The Primary Clinical Research Coordinator or designee will be responsible for registering the patient into OnCore at time of study entry, completing e-CRF based on the patient specific calendar, and updating the patient record until patient death or end of required study participation.

10.3 Data and Safety Monitoring Plan (DSMP)

The study's Data and Safety Monitoring Plan will be in compliance with the University of Minnesota Masonic Cancer Center's Data & Safety Monitoring Plan (DSMP), which can be accessed at http://z.umn.edu/dmsp.

For the purposes of data and safety monitoring, this study is classified as high risk. Therefore the following requirements will be fulfilled:

- At least quarterly review of the study's progress by the Masonic Cancer Center Data and Safety Monitoring Council (DSMC).
- The PI will comply with at least twice yearly monitoring of the project by the Masonic Cancer Center monitoring services.
- The PI will oversee the submission of all reportable adverse events per section 9.3 to the Masonic Cancer Center's SAE Coordinator, the University of Minnesota IRB, and the FDA.

In addition, at the time of the continuing review with the University of Minnesota IRB, a copy of the report with any attachments will be submitted to the Cancer Protocol Review Committee (CPRC).

IND Annual Reports

In accordance with regulation 21 CFR § 312.33, the Sponsor-Investigator will submit a progress report annually. The report will be submitted within 60 days of the anniversary date that the IND went into effect.

10.4 Study Monitoring

The investigator will permit study-related monitoring, audits, and inspections by the study's Principal Investigator and/or any designees, the local IRB, government regulatory bodies, and University of Minnesota compliance groups. The investigator will make available all study related documents (e.g. source documents, regulatory documents, data collection instruments, study data, etc.). The investigator will ensure the capability for inspections of applicable study-related facilities (e.g. pharmacy, diagnostic laboratory, etc.) will be available for trial related monitoring, audits, or regulatory inspections.

10.5 Record Retention

The investigator will retain study records including source data, copies of case report form, consent forms, HIPAA authorizations, and all study correspondence in a secured facility for at least 6 years after the study file is closed with the IRB and FDA.

11 Study Endpoints

